The aim of the present study is to investigate the effect of Bilateral Ultrasound-Guided intermediate cervical plexus Block combined with general anesthesia on the stress and inflammatory response in patients undergoing anterior cervical spine surgery (ACSS).

Objectives:

- *To compare between serum level of cortisol and interleukin-6 pre-operative and 24 hours post-operative in both groups.*
- *To identify Hemodynamics variables (mean arterial blood pressure and heart rate) peri-operatively.*
- *To assess the pain score during 1st 24 hours postoperative according to numeric pain rating scale (NPRS).*
- *To measure the incidence of complications within both groups.*

Hypothesis:

We hypothesize that intermediate cervical plexus block will offer a significant suppression of stress response and adequate post-operative analgesia in patients undergoing anterior cervical spine surgeries.

Ethical Considerations:

Our study will be conducted in Kasr El Aini Hospital, Cairo University after approval of the Research Ethics Committee. Full written informed consent will be obtained from the patients before inclusion in this study.

Methodology

Methodology

I. Study design:

A randomized controlled study.

II. Study setting and location:

The study will be conducted in the Neurosurgery operating rooms at Cairo University hospital.

III. Study population:

(66) Patients, aged from 18 to 65 years old, ASA physical status I-II, scheduled for anterior cervical spine surgery will be included in the study. Patients will be randomly allocated using concealed closed envelope method into one of two groups:

- Group A (n=33): will include the patients who will undergo bilateral ultrasound guided intermediate cervical plexus block after general anesthesia.*
- Group B (control group) (n=33): will include the patients who will undergo general anesthesia with conventional analgesia.*

IV. Eligibility Criteria

1. Inclusion criteria:

1. *ASA I & ASA II patients.*
2. *Age group: from 18 to 65 years old.*
3. *Patients undergoing anterior cervical discectomy or fixation.*
4. *Genders eligible for study: both sexes.*

2. Exclusion criteria:

- *Patient refusal.*
- *Patient Undergoing posterior fixation in addition to anterior.*
- *An allergy to local anaesthetics.*
- *Infection at block puncture site.*
- *Bleeding disorders (Coagulopathy: PTT > 40seconds, INR > 1.2, platelet count < 120 x 10³ / L.).*
- *Emergency surgeries & patients in sepsis.*

V. Study Procedures

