1. Randomization:

Patients will be randomly allocated by a computer-generated table into one of the study groups; the randomization sequence will be concealed in sealed opaque envelopes

2. Study Protocol:

Patients will be subjected to systematic preoperative assessment including history taking, physical examination and review of the results of routine investigations. NPRS (numeric pain rating scale) will be explained to all candidates where zero corresponds to no pain, and 10 is indicative of the worst unbearable pain. Upon arrival to the preparation room: An 18-gauge intravenous (IV) cannula will be inserted into a peripheral vein. Patients will be premedicated by intravenous 0.01 mg/kg midazolam and 10mg metoclopramide. Patients will be then transferred to the operating room where basic monitoring, Electrocardiography (ECG), Non-invasive Blood Pressure (NIBP) monitor and pulse oximetry will be attached.

General anesthesia will be induced in a standardized way with intravenous propofol 2.5mg/kg, fentanyl 1 μ /kg and atracurium 0.5mg/kg. Anesthesia will be maintained by inhalational isoflurane and intravenous atracurium 0.1mg/kg/20min.

Group A: The patient will be placed in a supine or semi-sitting position, with the head turned slightly away from the side to be blocked to facilitate operator access. The skin is disinfected and a linear-array ultrasound probe (Siemens ACUSON X300 Ultrasound System) is placed on the lateral neck, overlying the sternocleidomastoid muscle at the level of its midpoint (approximately the level

of the cricoid cartilage), Once the SCM has been identified, the transducer is moved posteriorly until the tapering posterior edge is positioned in the middle of the screen. At this point, an attempt should be made to identify the brachial plexus and/or the interscalene groove between the anterior and middle scalene muscles. The cervical plexus is visible as a small collection of hypoechoic nodules (honeycomb appearance) immediately superficial to the prevertebral fascia that overlies the interscalene groove.

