Once the plexus has been identified, the needle is passed through the skin, platysma, and investing layer of the deep cervical fascia, and the tip is placed adjacent to the plexus. . Following negative aspiration, 1–2 mL of normal saline is injected to confirm the proper injection site. Then after confirmation of safe needle position and absence of vascular spread, bupivacaine 0.25% (5–15 mL) is administered to envelop the plexus, and the block is repeated with the same technique on the opposite side.

(Figure 1).

[figure not shown]

Figure 1. *Cervical plexus (transverse view): desired distribution of local anesthetic (blue-shaded area) to nerve block the cervical plexus. Needle path: 1. ASM, anterior scalene muscle; CA, carotid artery; CP, cervical plexus; MSM, middle scalene muscle; SCM, sternocleidomastoid muscle.*

Group B: *Induction of general anesthesia as Group A, without performing intermediate cervical plexus block, intravenous morphine will be given in a dose of 0.1-0.2mg/kg to maintain intraoperative analgesia.*

All operations will be performed in the morning, taking into consideration circadian rhythm of hormone release. In both groups, venous blood samples to measure serum cortisol and interleukin-6 level will be collected before surgery as a baseline, then 24 hours post-operative. interleukin-6 is normally low and may be undetectable within 30-60 min after start of surgery while reaching maximum level at 24 hours post-operative.

During the intraoperative period; heart rate and mean arterial blood pressure will be recorded every 15 minutes throughout the surgery. Intravenous fentanyl bolus doses (0.5 µg/kg) will be adjusted to keep the HR and mean arterial blood pressure within 20% of the pre-induction values.

At the end of surgery, atracurium will be stopped and neuromuscular blockade will be reversed with intravenous neostigmine 0.04 mg/kg and 0.01 mg/kg atropine and endotracheal tube will be removed.

After operation, patients will be transferred to post anesthesia care unit (PACU) for complete recovery and monitoring. A standard postoperative analgesia regimen will be prescribed as intravenous paracetamol 1gm every 8 hours. Intravenous morphine 0.05 mg/kg will be given as a rescue analgesic dose if numeric analogue score was ≥ 3 . Metoclopramide 0.15 mg/kg IV will be prescribed for patients complaining of nausea or vomiting.

The maximum dose of morphine that will be given is 20 mg/24 hrs.

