The block will be considered a failed block if the patient required more than two doses of rescue analgesia in the first hour postoperatively.

Measurement tools

- *Demographic data: age, sex, body mass index (BMI).*
- *Serum cortisol and interlukien-6 pre-operative and 24 hours post-operative.*
- *Hemodynamics {heart rate, arterial blood pressure (systolic, diastolic and mean blood pressure)} will be recorded at the following intervals: baseline reading , Intraoperative 15 minutes post-intubation (pre-block), 15 minutes after the block/administration of morphine and then every 15 minutes throughout the surgery, and postoperative at 1,6,12, 24 hours..*
- *NPRS score at 15, 30, and 60 min, 6, 12, 24 hours post-operatively.*
- *Number of patients in each group who need intraoperative additional analgesic doses of fentanyl and total fentanyl dose for each patient.*
- *Total postoperative analgesic requirements.*
- *Failure rate of the block (the block will be considered a failed block if the patient required more than two doses of rescue analgesia in the first hour postoperatively).*

VI. Study outcomes

1. Primary outcomes:

- *The serum cortisol level 24 hours postoperatively.*

2. Secondary outcomes:

- *The serum interleukin-6 24 hours postoperatively.*
- *Intraoperative hemodynamics {heart rate, arterial blood pressure (systolic, diastolic and mean blood pressure)}*
- *Intraoperative additional fentanyl requirements.*
- *NPRS score postoperative during 1st 24 hours. 15, 30, and 60 min, 6, 12, and 24 hours after surgery.*
- *Time to first postoperative analgesic request (duration of analgesia).*
- *Block failure rate.*
- *Incidence of complications. (Nerve injury, Hematoma formation, LA toxicity, intravascular injection.*
- *Block failure: The block will be considered a failed block if the patient required more than two doses of rescue analgesia in the first hour postoperatively.*

Statistical Analysis

Statistical Analysis

I. Sample size

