Our primary outcome is the serum cortisol level 24 hours postoperatively. In a previous study, the serum cortisol level after 24 hours was 21.8 ± 4.7 micrograms per deciliter (mcg (ref) after lumbar fixation surgeries. We calculated a sample size that could detect a mean difference of 20% between both study groups. MedCalc Software version 14 (MedCalc Software bvba, Ostend, Belgium) was used to calculate the sample size 60 patients (30 Patient per group) at least were estimated to have a study power of 95% and an alpha error of 0.05. This number will be increased to 66 patients (33 patients per group) to compensate for possible dropouts.

Sample size calculation was performed guided by power of 95%, confidence level of 95 %.(8)

II. Statistical analysis

For data analysis, the Statistical Package for Social Science (SPSS) software, version 26 for Microsoft Windows (SPSS Inc., Chicago, IL, USA) will be used. The Chi squared test will be used to examine categorical data, which will be given as frequency (percent). The Shapiro-Wilk test will be used to verify for normality in continuous data, and the results will be provided as mean (standard deviation) or median (interquartile range) as appropriate. Depending on the data's normality, the unpaired t test or the Mann Whitney test will be used to assess it. Repeated measures will be examined using analysis of variance (ANOVA), with post-hoc pairwise comparisons using the Bonferroni tests. A P value less than 0.05 will be considered statistically significant.

References

References:

1. Arfanis K, Fioratou E and Smith A: Safety culture in anaesthesiology: Basic concepts and practical application. *Best Pract Res Clin Anaesthesiol* 25: 229-238, 2011.

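### The primary outcome is 24-hour serum cortisol, but patients with recent corticosteroid use or known adrenal or pituitary disease are admitted, and steroid exposure is neither recorded nor handled in the analysis

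*Combined protocol and SAP*

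**What the plan says.** Section VI, Study outcomes, names one primary outcome: "The serum cortisol level 24 hours postoperatively". The sample size rests on an earlier lumbar fixation study in which "the serum cortisol level after 24 hours was 21.8 ± 4.7 micrograms per deciliter".

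Section IV lists six exclusions: refusal, added posterior fixation, local anaesthetic allergy, infection at the puncture site, bleeding disorders, and "Emergency surgeries & patients in sepsis". Inclusion is limited to ASA I-II and age 18 to 65.

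Section V plans a "systematic preoperative assessment including history taking, physical examination" and review of routine tests, without naming steroid or endocrine history. Of the drugs it names, those relevant to nausea involve no steroid: "Patients will be premedicated by intravenous 0.01 mg/kg midazolam and 10mg metoclopramide", and later "Metoclopramide 0.15 mg/kg IV will be prescribed for patients complaining of nausea or vomiting". No steroid is scheduled anywhere, and none is ruled out. Blood samples "will be collected before surgery as a baseline, then 24 hours post-operative", and all operations are held in the morning because of the daily hormone rhythm.

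The Measurement tools list includes "Serum cortisol and interlukien-6 pre-operative and 24 hours post-operative" but no steroid exposure. Statistical Analysis II compares the arms by an unpaired t test or a Mann-Whitney test, depending on normality. It mentions no baseline covariate and no handling of exposed patients.

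**The concern.** A corticosteroid, or disease of the pituitary-adrenal axis, can change serum cortisol whatever the block does. In such a patient the primary outcome may show little or none of the block's effect. The plan already controls one influence on cortisol unrelated to the block, time of day, but says nothing about this more direct one.

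Two things are at stake. Affected patients who enter before allocation dilute the difference between arms and widen the spread, which costs power. If any steroid were given after allocation, randomisation would not balance it, and no required record would let anyone check whether its use differed by arm. IL-6, a secondary outcome, may be affected too.

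**Working it through.** **Inputs from Statistical Analysis I.** Control mean 21.8 and SD 4.7 mcg/dL; target difference 20%, so 0.20 × 21.8 = 4.36 and block-arm mean 21.8 − 4.36 = 17.44; alpha 0.05 (two-sided assumed, as the plan does not say); power 95%; 30 per arm, raised to 33 for dropouts.

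**Assumptions, not in the documents.** A share f of patients in each arm is affected. Their 24-hour cortisol is lowered to a mean (SD) of 5 (2), 10 (3) or 14 (4) mcg/dL, with no block effect.

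**1. Reproduce the plan's figure.** n per arm = 2 × (1.960 + 1.645)² × 4.7² / 4.36² = 2 × 12.99 × 22.09 / 19.01 = 30.2, so 31 per arm and 62 in total against the stated 60. With the exact t distribution, power is 94.2% at 30 per arm and 96.0% at 33. The stated size is reproduced to within two patients. The only stated reason for the increase to 66 is dropout, so there is no allowance for affected patients.

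**2. Dilution and spread.** The expected difference becomes 4.36 × (1 − f). Each arm's variance becomes (1 − f) × 4.7² + f × s² + f(1 − f) × (arm mean − m)², where m and s are the mean and SD of affected patients. Example with f = 5%, m = 5, s = 2:
- control: 20.99 + 0.20 + 0.0475 × 16.8² = 34.59
- block: 20.99 + 0.20 + 0.0475 × 12.44² = 28.54
- pooled SD: √31.56 = 5.62, against 4.7 planned

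For m = 10 and m = 14 the pooled SD at 5% is 5.10 and 4.85.

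**3. Power under the planned test rule.** 10,000 simulated trials per setting; Mann-Whitney if Shapiro-Wilk p < 0.05 in either arm, otherwise the t test. Monte Carlo standard error is up to about 0.4 point. Power (%) is shown for affected means of 5 / 10 / 14.

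| Affected | Expected difference | 30 per arm | 33 per arm |
|---|---|---|---|
| 0% | 4.36 | 94.0 | 95.7 |
| 1% | 4.32 | 91.8 / 92.7 / 93.5 | 93.9 / 95.2 / 95.6 |
| 2% | 4.27 | 90.2 / 91.4 / 92.5 | 92.1 / 93.8 / 94.4 |
| 3% | 4.23 | 87.8 / 90.6 / 91.8 | 91.3 / 92.4 / 93.9 |
| 5% | 4.14 | 84.2 / 87.7 / 90.1 | 87.9 / 90.0 / 92.6 |
| 10% | 3.92 | 75.2 / 79.4 / 85.8 | 80.4 / 82.4 / 87.9 |

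**4. Chance imbalance.** Each simulated patient is affected independently, so the number affected already varies between arms. Imbalance by chance is inside these figures.

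**5. Cross-check with another model.** Affected patients are set at 75%, 50% or 25% of 21.8 with SD 4.7, and a t test alone is used. At 30 per arm, power is 91 / 87 / 80% at 5% affected and 87 / 79 / 65% at 10%. The low end is lower than in the table partly because this model never switches to the rank test.

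**6. Omitting affected patients.** At 30 per arm, dropping those affected before allocation gives power of 93-94% at 1-5% affected and 91% at 10%, without baseline adjustment.

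**The case against.** The strongest reply is that the size rests wholly on assumed figures. Nothing in the documents shows that 5-10% of elective ASA I-II patients aged 18 to 65 would be affected. At 1-3% the loss at 30 per arm is about 0.5-6 points, much of which a trial sized for 95% power can absorb. The model also gives affected patients no block effect at all, which is the pessimistic end, and the loss is smaller if the study behind the SD of 4.7 already included such patients. This stands, and it limits the weight of the point.

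The plan also has partial safeguards. The first objective compares pre-operative with 24-hour values in both groups, and the analysis section provides ANOVA for repeated measures. Both bear on suppression already present at baseline. Neither is stated as the primary analysis, and a baseline sample cannot show a steroid given after it was drawn.

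A reader might infer that steroids will be given after allocation, perhaps unequally by arm. The documents do not support that: induction is standardised, metoclopramide is the named drug for both premedication and nausea, and no steroid appears. What remains is only that such use would go unrecorded, and the calculations above do not quantify it.

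**Conclusion.** The point holds as a precision and record-keeping gap in a trial whose primary outcome is cortisol. The exclusions admit patients whose 24-hour cortisol may not reflect the block, and the plan neither records nor handles steroid exposure. Under the stated assumptions, power at 30 per arm falls from 94% to about 88-94% at 1-3% affected, 84-90% at 5% and 75-86% at 10%. The loss is small at 1-3% and becomes material at about 5% or more. Prevalence and degree of suppression are unknown, only lowered cortisol was modelled, and adrenal or pituitary disease has no separate estimate.

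Two stronger readings should be resisted. The primary comparison is not shown to be biased, because randomisation balances pre-operative exposure in expectation. Chance imbalance between small arms is not a further harm on top of the power loss, because the power figures already include it. Nor do the documents contradict themselves here; this is an inexpensive improvement to the design.

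**What to change.** 1. Add an exclusion for systemic or epidural corticosteroid use within an investigator-defined window before surgery, and for known adrenal or pituitary disease. Check it at the history taking already planned.
2. Record any perioperative steroid (drug, dose, time) on the case report form and report it by arm.
3. Keep all randomised patients in the primary analysis.
4. Prespecify two separate supporting analyses of cortisol and IL-6: (a) ANCOVA adjusting for the baseline value already collected, in all randomised patients; (b) an analysis omitting only patients found to have had exposure or disease before allocation. Keeping them apart allows a changed result to be traced to one cause.
5. Describe post-allocation exposure by arm and do not drop those patients, since dropping them would break the randomised comparison.

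The cost is one exclusion line, one form line, a little more analysis work and a slightly smaller eligible pool. Exclusion comes before randomisation, so the target of 66 can stand. No sample, visit or endpoint changes. Whether steroids should be given is a clinical matter and is not addressed here.

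### The pre-operative/24-hour interleukin-6 objective has no analysis beyond untransformed ANOVA and no rule for undetectable results (minor, secondary outcome)

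*Combined protocol and SAP*

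**What the plan says.** All references are to the combined protocol and SAP.

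- **Objectives.** The first objective is: "To compare between serum level of cortisol and interleukin-6 pre-operative and 24 hours post-operative in both groups".
- **V. Study Procedures, 2. Study Protocol.** Blood samples "will be collected before surgery as a baseline, then 24 hours post-operative", so each patient has one pair of values. The same paragraph says that "interleukin-6 is normally low and may be undetectable within 30-60 min after start of surgery", and it puts the peak at 24 hours after the operation.
- **VI. Study outcomes, 2. Secondary outcomes.** The listed outcome is the later value alone: "The serum interleukin-6 24 hours postoperatively". Change from baseline is not listed.
- **Statistical Analysis, II.** "The Shapiro-Wilk test will be used to verify for normality in continuous data", and then: "Depending on the data's normality, the unpaired t test or the Mann Whitney test will be used to assess it". For repeated measures there is one sentence: "Repeated measures will be examined using analysis of variance (ANOVA), with post-hoc pairwise comparisons using the Bonferroni tests". It names no variable.

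The plan gives no transformation, no non-normal alternative for repeated measures, no interleukin-6 assay limit, no value for undetectable results and no missing-data rule.

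**The concern.** The objective uses both interleukin-6 samples, and ANOVA is the only method the plan offers for paired or repeated values. The plan's own description suggests that ANOVA on the raw scale may fit this marker badly. The marker starts low and rises to a peak, so some pre-operative results may fall below the assay limit, and the 24-hour values may have a long right tail.

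Two things follow. On the raw scale, a few very high 24-hour values can dominate the variance and weaken the comparison between arms. And an undetectable result has no number until someone assigns one. If it is entered as missing, a standard repeated-measures ANOVA uses complete pairs only, so the patient's valid 24-hour value is lost too. As written, that choice could be made after the results are known.

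Interleukin-6 is the only inflammatory marker measured in support of an aim that covers both the stress and the inflammatory response.

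**Working it through.** **The plan's own figure.** The plan states no power or sample size for interleukin-6. Its one calculation is for cortisol: mean 21.8, SD 4.7, difference 20%, power 95%, alpha 0.05 (two-sided assumed).

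- Difference = 0.20 × 21.8 = 4.36.
- n per arm = 2 × (1.960 + 1.645)² × 4.7² / 4.36² = 30.2, rounded up to 31. Power at 30 per arm is 94.9% (normal approximation).

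This agrees with the stated 30 per arm to within one patient, and nothing below changes it.

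**What raw ANOVA tests here.** With two arms and two times, the group-by-time test is the two-sample t test on the raw change (24-hour minus baseline). It can therefore be compared directly with a log-scale t test, Mann-Whitney or ANCOVA.

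**Assumed inputs (none are in the documents).** Lognormal values, 30 per arm, geometric mean rising 10-fold from baseline to 24 hours (5-fold also tried), and baseline/24-hour correlation 0.3 on the log scale. Simulations used 4,000 trials per setting.

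**Step 1: skew alone, nobody dropped.** Undetectable baselines are set to half the assay limit. The A/B ratio is 0.6 at log-SD 0.7 and 0.9. At 0.4 it is 0.744, chosen for about 80% power on the log scale.

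| 24-hour log-SD | Log t test, 24 h | Mann-Whitney, 24 h | Raw change, all kept | Loss, raw against log |
|---|---|---|---|---|
| 0.4 | 79–80% | 77–78% | 78–79% | 0 to 1 point |
| 0.7 | about 80% | 77–78% | 72–74% | about 6 (6 to 8) |
| 0.9 | 57–59% | 54–56% | 45–47% | about 12 (11 to 13) |

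Power is lower at log-SD 0.9 for every method because the ratio is held at 0.6 while the spread grows.

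**Step 2: the cost of lost pairs, without skew.** Set the standardised effect for 80% power at 30 per arm: d = (1.960 + 0.842) × √(2/30) = 0.723. With m complete pairs per arm, power = Φ(d × √(m/2) − 1.960).

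- 10% lost, m = 27: 75.7%, a loss of 4 points.
- 20% lost, m = 24: 0.723 × √12 − 1.960 = 0.546, giving 70.7%, a loss of 9 points.
- 40% lost, m = 18: 0.723 × √9 − 1.960 = 0.210, giving 58.3%, a loss of 22 points.

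**Step 3: skew and lost pairs together (simulated, A/B ratio 0.6).**

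- Log-SD 0.7: 63–64% with 20% undetectable and dropped, 50–51% with 40%. Against about 80%, that is a loss of about 16 and 30 points.
- Log-SD 0.9: 38% and 29–31%. Against about 58%, that is a loss of about 20 and 28 points.

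From the mildest case in step 2 to the worst in step 3, the loss is about 10 to 30 points at 20 to 40% undetectable.

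**Step 4: using the baseline.** With the effect set for about 80% power on the log t test, log-scale ANCOVA with half-limit substitution gave 82–84%, a gain of about 2 to 4 points. Testing the log change instead gave only 48–70%, because noise in the baseline is carried in full into the difference.

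**The case against.** The case against is substantial, and most of it stands.

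- **The listed outcome is already handled.** It is the 24-hour level, which the protocol expects to be at its peak. Normality is checked, Mann-Whitney is the fallback, and undetectable baselines remove nobody. That test is within about 2 to 4 points of the log t test. This stands in full.
- **Interleukin-6 is not named under ANOVA.** Bonferroni pairwise comparisons suit the many-timepoint haemodynamic and pain scores better than a single pair of times. This stands as a point of wording. But the first objective uses the pair, and no other paired or repeated-measures method is given.
- **A reader might infer that the plan discards patients with undetectable baselines.** It does not say so. With any substituted value nobody is lost, and after a large rise the raw change hardly depends on which value is used. What remains is that the plan does not rule dropping out.
- **A reader might infer that the protocol predicts undetectable pre-operative samples.** The sentence concerns the period up to 30–60 minutes into surgery, when no sample is drawn. Low baselines are a fair inference from the marker being normally low; the fraction below the assay limit is unknown.
- **No bias follows.** Baseline precedes treatment, so dropping such patients would cost precision and narrow the population, but should not in itself bias the comparison of arms. Medians with interquartile ranges are also planned, so the data would not go undescribed.

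**Conclusion.** The point holds as a minor one. The plan sets a pre/24-hour interleukin-6 objective and leaves it with raw-scale ANOVA as the only available method and no rule for undetectable results.

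With all patients kept, the cost ranges from negligible under mild skew to about 12 points at log-SD 0.9. The 10 to 30 points are conditional on 20 to 40% of baselines being undetectable and treated as missing, and should not be read as the expected loss. The documents give no interleukin-6 mean, spread, assay limit or non-detect rate, so every power figure for this marker rests on the assumptions above. They do not support a claim that the trial will lose much of its power for interleukin-6, or that the listed 24-hour outcome is analysed unsoundly.

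**What to change.** In Statistical Analysis, II, add an interleukin-6 paragraph, fixed before any results are seen:

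- For the pre/24-hour pair, replace raw-scale repeated-measures ANOVA with ANCOVA: log 24-hour interleukin-6 compared between arms, adjusted for log baseline.
- Report the A/B ratio of geometric means with a 95% CI.
- Include every patient with a 24-hour sample.
- State the assay limit, and set any result below it to one pre-stated value (for example half the limit), never to missing.
- Keep Mann-Whitney on the 24-hour value as the check.
- Do not use the log change in place of ANCOVA (step 4 of the working).

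The cost is SAP wording only: no new samples and no change to sample size. The downsides are that the result is a ratio, which some readers find less direct than a difference, and that the substitute value is arbitrary, though it should mostly affect baselines.

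### The chi-squared rule does not suit rare or block-only complications at 33 per arm, and opioid harms and Group B's intraoperative morphine dose are not listed variables

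*Combined protocol and SAP*

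**What the plan says.** **Complications.** The Objectives include "To measure the incidence of complications within both groups". Study outcomes names four: nerve injury, hematoma, local anaesthetic toxicity and intravascular injection. The parenthesis that holds the list is not closed. The Statistical analysis section reports categorical data as frequency and percent and tests them by chi-squared; it names no exact test.

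**Intraoperative opioid.** Under Study Procedures, Group B has no block, and "intravenous morphine will be given in a dose of 0.1-0.2mg/kg to maintain intraoperative analgesia". Measurement tools lists, for intraoperative opioid, "Number of patients in each group who need intraoperative additional analgesic doses of fentanyl and total fentanyl dose for each patient". Morphine appears there only as a time marker for hemodynamics: "15 minutes after the block/administration of morphine and then every 15 minutes throughout the surgery".

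**Opioid harms.** The background before Aim of the work names nausea, vomiting and respiratory depression as undesirable in patients already at risk of airway problems. Study Procedures provides an antiemetic that "will be prescribed for patients complaining of nausea or vomiting". None of the three harms is a listed measurement or outcome.

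**Postoperative rescue.** The Hypothesis claims "adequate post-operative analgesia in patients undergoing anterior cervical spine surgeries". Study Procedures states: "Intravenous morphine 0.05 mg/kg will be given as a rescue analgesic dose if numeric analogue score was" 3 or more. It then adds: "The maximum dose of morphine that will be given is 20 mg/24 hrs". The postoperative analgesic total is in Measurement tools but not among the outcomes. Time to first request and first-hour block failure are secondary outcomes.

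**The concern.** The complications table is meant to describe both arms, but as listed it leans towards harms of the block. Two of its four rows can be filled only by Group A. The harms of the control arm's opioid, which the background uses to motivate the trial, have no row at all. A reader could not set block harms against opioid harms.

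The one test named for these rows is a large-sample approximation applied to counts that will probably be small. A handful of events in one arm could be reported as significant when an exact test would not support it.

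Pain scores raise a smaller, related issue. Rescue morphine is triggered by the score and so affects later scores. Similar readings at 6, 12 and 24 hours could mean equal pain control or unequal rescue. Telling these apart needs the rescue dose with its time, and the plan lists only a total.

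**Working it through.** **Inputs.** 33 per arm, 66 in all, or 30 per arm before the dropout allowance (Sample size); significance level 0.05 (Statistical analysis); intraoperative morphine 0.1-0.2 mg/kg in Group B and rescue morphine 0.05 mg/kg (Study Procedures). The plan gives no expected complication rates, so there is no figure of its own to reproduce here.

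**1. Chi-squared against an exact test, x events in one arm and 0 in the other.**
- Chi-squared without correction: 66 × (33x)² / [33 × 33 × x × (66 − x)]. For x = 4 this is 66 × 132² / (33 × 33 × 4 × 62) = 4.26 on 1 degree of freedom, p = 0.039.
- Fisher, two-sided: 2 × C(33,4) / C(66,4) = 2 × 0.0568 = 0.114.

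| Events | Chi-squared p | Fisher p |
|---|---|---|
| 3 vs 0 | 0.076 | 0.238 |
| 4 vs 0 | 0.039 | 0.114 |
| 5 vs 0 | 0.020 | 0.053 |
| 6 vs 0 | 0.010 | 0.024 |

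At 4 vs 0 and 5 vs 0 the two tests fall on opposite sides of 0.05. The plan does not say whether a continuity correction applies. With it, 4 vs 0 gives 66 × (132 − 33)² / (33 × 33 × 4 × 62) = 2.40, p = 0.122, so the choice alone changes the conclusion.

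**2. When the approximation is usually accepted.** The expected count per arm is total events × 33/66. The usual minimum of 5 needs 10 events: 10/66 = 15.2% overall. For a block-only event all 10 must be in Group A: 10/33 = 30.3%.

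**3. Block-only events.** The Group B count is zero by design, so a between-arm test does not compare two risks. The useful figure is the exact interval in Group A. With no events, the upper limit of the two-sided 95% interval is 1 − 0.025^(1/33) = 10.6%, or 1 − 0.025^(1/30) = 11.6% with 30 patients.

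**4. Size of the unlisted morphine dose.** 0.1/0.05 = 2 and 0.2/0.05 = 4, so each Group B patient receives the equivalent of 2 to 4 rescue doses during surgery. This lies outside both the fentanyl total and the postoperative total.

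**5. Rescue and pain scores.** Pain is read at 15, 30 and 60 minutes and at 6, 12 and 24 hours. The only outcome that counts rescue doses covers the first hour, so three of the six readings fall after it. Time to first request shows whether any rescue came before a reading, but not how much.

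**The case against.** **The fentanyl outcome.** A reader might infer that it is invalid because it leaves out morphine. The documents do not support that. The outcome is labelled as additional fentanyl, that is, need beyond the assigned analgesia, and nothing claims a comparison of total opioid. What stands is that the dose given should be listed, because the permitted range is two-fold.

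**Postoperative rescue.** A reader might infer that rescue is ignored. It is not: the total is collected, and two secondary outcomes depend on rescue. Promoting the total to an outcome would be mostly relabelling, and a 24-hour total would not show rescue before the 6- and 12-hour readings. What stands is the need for dose times.

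**The morphine limit.** A reader might infer that rescue is capped lower in Group B. The limit follows the postoperative instructions, so a purely postoperative reading is natural. The wording does not exclude the other reading, and nothing shows how often patients would reach the limit. Only the ambiguity stands.

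**Opioid harms.** These are background, and no objective claims fewer of them. The open parenthesis may also mean that the list is incomplete. However, Measurement tools omits them too, and the objective covers both arms.

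**The test.** The chi-squared sentence is generic, and measuring incidence does not require a test. Averaged over all possible tables (two binomial arms of 33, adding the probability of every table with p < 0.05), uncorrected chi-squared rejects 3.3% of the time at a 5% risk in both arms and 5.6% at 10%, so its long-run error is not grossly inflated. Fisher's test is conservative. What stands is that the p-value for a particular sparse table can mislead: given 4 events in all, a 4-0 split in either direction has probability 0.114, not 0.039.

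**Conclusion.** The point holds as a low-cost improvement to secondary outcomes. At 33 per arm the only test named for complications can call 4 vs 0 or 5 vs 0 significant when an exact test does not. Two of the four listed complications are not comparable between arms. That statement rests on two assumptions: Group B receives no local anaesthetic, such as wound infiltration (none is described), and intravascular injection means injection of local anaesthetic. Nerve injury and hematoma can follow surgery in either arm.

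The opioid harms named in the background, and an intraoperative morphine dose worth 2 to 4 rescue doses in Group B only, are not listed for collection. The dose may well be on the anaesthetic chart, but the plan does not commit to reporting it.

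A reader might infer that these gaps weaken the main result. They do not: the primary outcome is serum cortisol at 24 hours, and neither its analysis nor the sample size depends on anything here.

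**What to change.** 1. In Statistical analysis, use Fisher's exact test for between-arm comparisons of sparse complications such as nerve injury and hematoma.
2. Report local anaesthetic toxicity and intravascular injection as Group A frequency and percent with exact 95% confidence intervals and no between-group test.
3. Record nausea and vomiting (or antiemetic use), and respiratory depression with a stated definition, in both arms as descriptive outcomes.
4. List the intraoperative morphine dose actually given and report it beside fentanyl, drug by drug. The documents give no conversion ratio, so any combined total should be a descriptive sensitivity analysis over a stated range.
5. Record the time of each rescue dose, and report rescue before the 6-, 12- and 24-hour readings beside the pain scores.
6. Reconcile Study Procedures on whether the 20 mg/24 hrs morphine limit includes Group B's intraoperative morphine, since this affects how the rescue total is read. No limit is proposed here.

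The cost is an amendment to the variable and outcome lists and a few form fields, with no extra visits, samples or patients. The drawback is more secondary outcomes, so the additions should be labelled descriptive. The change is best made before enrolment, because dose times and events not captured as they occur may be hard to recover.
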